3.1. Safety and Tolerability Objective

To describe the safety, tolerability and exposure-toxicity relationship of delpazolid (DZD) given over 16 weeks, in combination with standard-dose BDQ, DLM and MXF, compared to standard dose BDQ, DLM and MXF alone.

The aim is to identify the optimal dose of DZD to be used in subsequent studies that provides the best efficacy at acceptable safety of the drug when given daily over 4 months in patients with newly diagnosed, uncomplicated, smear-positive, drug-sensitive, pulmonary tuberculosis.

3.2. Efficacy Objectives

3.2.1. Primary Efficacy Objective:

To establish an exposure-response model for DZD, given over 16 weeks in combination with standard-dose BDQ, DLM and MXF, on the change in liquid culture MGIT time to positivity (TTP).

3.2.2. Secondary Efficacy Objectives:

- To assess dose and exposure-response relationships for DZD, based on secondary efficacy endpoints, including month-2
 culture status in liquid media and on solid media, and time to culture conversion in liquid and on solid media.
- To assess the relative efficacy of increasing DZD doses compared to the background regimen without DZD, based on primary and secondary efficacy endpoints.
- To assess the proportion of patients who suffer relapse within 12 months post randomization, out of those patients completing 16 weeks of therapy and achieving sustained sputum culture conversion, defined as two successive negative liquid media cultures at or before WK08, with no positives to follow until the week 16 visit.

3.3. Pharmacokinetics Objectives

3.3.1. Primary Pharmacokinetics Objective

• To describe the pharmacokinetics (PK) of DZD through development of a population PK model.

3.3.2. Secondary Pharmacokinetics Objective

To describe the PK of BDQ, DLM and MXF including their main metabolites.

3.4. Mycobacteriology Identification and Characterization Objectives

 To assess the minimum inhibitory concentrations (MIC) of BDQ, DLM, MXF, DZD of the infecting strain, at baseline and on representative isolate(s) grown at or after WK08.

- To investigate the frequency of acquired mutations in the infecting strain over treatment.
- In participants with recurrent disease: comparison of initial and recurrence isolate by whole genome sequencing to discriminate relapse from reinfection.

4. Trial Design

4.1. Overview

This will be an open label Phase IIb dose-finding, randomized, controlled study with a duration of 16 weeks of experimental therapy of DZD – Bedaquiline/Delamanid/Moxifloxacin (BDM) in adult participants with newly diagnosed, smear positive, uncomplicated, drug sensitive pulmonary tuberculosis (TB) to evaluate the safety, efficacy, tolerability, pharmacokinetics and exposure/response-relationship of different doses of delpazolid in combination with bedaquiline, delamanid and moxifloxacin.

Participants will be randomized to one of five arms containing BDM with different doses of DZD:

- Arm 1 (D0): 15 participants will receive 0 mg of DZD.
- Arm 2 (D400): 15 participants will receive 400 mg DZD orally once daily.
- Arm 3 (D800-OD): 15 participants will receive 800 mg DZD orally once daily.
- Arm 4 (D1200): 15 participants will receive 1200 mg DZD orally once daily.
- Arm 5 (D800-BD): 15 participants will receive 800 mg DZD orally twice daily.

Participants will visit the study clinic on a weekly basis for sputum collection, safety monitoring and receipt of study medication. After the completion of 16 weeks of experimental treatment, participants in the experimental arms, who did not achieve two successive negative liquid media cultures with the first at or before WK08, with no positives to follow by the week 16 visit, will be referred to their local health care facility to complete their course of anti-TB treatment according to the national TB program.

4.2. Randomization

Randomization will be implemented after all screening results are available for participants who have given informed consent and who have been found eligible for participation. Participants will be randomized by centralized allocation to a predefined list.

Participants will be allocated using the Internet-Based Randomization service system: RANDOMIZE.NET. Participant randomization will be stratified by bacterial load in sputum as measured by GeneXpert, cycle threshold (≥ 16, < 16), site (seven sites have been activated: The Aurum site, UCTLI, TASK Eden, Clinical HIV Research Unit (CHRU), KCRI/KIDH, the Ifakara site and the NIMR-MMRC site), and HIV status (positive, negative). Each site will have its own account and the allocation result will be generated by the web system immediately based on the minimization randomization algorithm. The minimization algorithm allocates the patient to the treatment arm with the lowest allocation proportion.

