#### **10.2** Trial population

Participants will be randomized to one of five arms containing a BDM backbone with different doses of DZD, ranging from 0mg DZD (no DZD present in the regimen) up to 1,600mg (800mg BD). 75 participants will be randomized into this study, with 15 participants per arm.

In the case of unforeseen delays or a rate of dropouts or non-evaluable participants that is higher than anticipated, it may be necessary to recruit more participants than planned into the entire study (see sample size considerations, Chap. 15.1).

Participants will be randomised by centralized allocation, using a probabilistic minimisation algorithm, which will stratify participants by bacterial load in sputum as measured by GeneXpert cycle threshold, site and HIV status.

Participants will visit the study clinic on a weekly basis for sputum collection, safety monitoring and receipt of study medication.

After the completion of 16 weeks of experimental treatment, participants in the experimental arms, who did not achieve two successive negative liquid media cultures with the first at or before WK08, with no positives to follow by the week 16 visit, will be referred to their local health care facility to complete their course of anti-TB treatment according to the national TB program.

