# 13.5 Procedures to assign participants to treatment groups

Patients who have given informed consent and who have been found eligible for participation (meeting all inclusion criteria and no exclusion criterion) based on results from screening visit, will be randomly assigned to one out of five treatment arms with a 1:1:1:1:1 allocation. Randomization must be performed when all screening results are available but not before eligibility for study participation is proven.

Randomization will be performed through centralized assignment of patients by means of an Interactive Web Response System (IWRS), a web-based randomization system. Patient characteristics will be used to balance the composition of the treatment arms with regards to prognostic factors.

These characteristics will be:

- site
- HIV status
- bacterial load in sputum as measured by GeneXpert cycle threshold

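### SAP 4.2 describes minimisation with no random element, and also a predefined list, where the protocol specifies probabilistic minimisation; the algorithm actually used should be documented and its factors carried into the arm comparisons

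*SAP*

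**What the plan says.** Protocol 10.2 (Trial population) has participants "randomised by centralized allocation, using a probabilistic minimisation algorithm", with Ct, site and HIV status as the factors. Protocol 13.5 adds that eligible patients "will be randomly assigned to one out of five treatment arms with a 1:1:1:1:1 allocation" through a central web system, with the same three factors. Neither section gives an assignment probability.

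SAP 4.2 (Randomization) makes three statements:

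- First, on what patients are allocated to: "Participants will be randomized by centralized allocation to a predefined list".
- Second, on how and when a result arises: "the allocation result will be generated by the web system immediately based on the minimization randomization algorithm".
- Third, on which arm is then given: "The minimization algorithm allocates the patient to the treatment arm with the lowest allocation proportion".

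The factor levels are in the same section: two for Ct, "cycle threshold (≥ 16, < 16"; seven for site, "seven sites have been activated"; and two for HIV status. The SAP gives no assignment probability, imbalance measure, factor weights or tie-break rule. Its document history shows a first version, dated 13 February 2023 and written against protocol version 2.1, so no amendment explains the difference.

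**The concern.** Probabilistic minimisation favours the arm that would reduce imbalance but leaves some chance of any other arm. The SAP sentence, taken as written, always gives the favoured arm. A predefined list is a different device again: it is fixed before patients arrive, whereas minimisation computes each allocation from the patients already entered.

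Predictability matters because the trial is open label (protocol 13.6) and each site sees its own past allocations while site is a balancing factor. Someone who can guess the next arm can let the guess influence whom to enrol or when, and several exclusion criteria in protocol 10.4 rest on investigator judgement. Blinding the laboratory and the sponsor medical expert protects outcome assessment, not enrolment.

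The analysis is also affected. Arm comparisons after minimisation should normally account for the balancing factors, and a re-randomisation test cannot be programmed until the true algorithm is written down.

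**Working it through.** The plan states no figure for predictability, so there is nothing of its own to reproduce. The check is a comparison of the texts plus an illustrative simulation.

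**Inputs from the documents.** 75 participants, 5 arms (75/5 = 15 per arm), 7 sites, 2 Ct levels, 2 HIV levels.

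**Assumptions, not in the documents.** 30% HIV-positive, Ct split 50:50, equal site sizes, ties broken at random, favoured-arm probability p of 0.7 to 0.9 for the protocol's rule. HIV prevalence and Ct split were not varied.

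**Method.** 2,000 simulated trials per setting. The score for each arm is its count at the patient's site, plus its count at the patient's HIV level, plus its count at the patient's Ct level. The lowest-scoring arm is assigned with probability p, otherwise one of the other four at random. The literal SAP rule is p = 1. An own-site guess picks the arm least used so far at that site. A full-knowledge guess uses the whole minimisation table.

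| Rule | Own-site guess correct | Full-knowledge guess correct |
|---|---|---|
| Simple randomisation | 20.1% | 20.1% |
| Marginal counts, p = 1 | 37.8% | 70.7% |
| Marginal counts, p = 0.9 | 35.5% | 65.9% |
| Marginal counts, p = 0.8 | 33.2% | 60.8% |
| Marginal counts, p = 0.7 | 30.6% | 55.0% |
| Overall arm totals, p = 1 | 21.4% | 45.5% |
| Overall arm totals, p = 0.8 | 21.5% | 42.7% |

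With marginal counts and p = 1, 50.4% of assignments are fixed in advance, because one arm alone has the lowest score. With any random element none is.

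**Check on one row.** With overall totals and p = 1, each run of five patients fills each arm once. A fully informed guesser is right with probability (1/5 + 1/4 + 1/3 + 1/2 + 1)/5 = 2.283/5 = 45.7%, against 45.5% simulated.

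**Size of the difference.** For own-site guessing, p = 1 adds 37.8 − 35.5 = 2.3 points over p = 0.9, 4.6 over p = 0.8 and 7.2 over p = 0.7. At p = 0.8 the excess over chance is already 33.2 − 20 = 13.2 points, of the 37.8 − 20 = 17.8 reached at p = 1. With 3 sites instead of 7, own-site guessing is 41.3% (p = 1), 36.8% (p = 0.8) and 34.2% (p = 0.7).

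**Covariates planned.** The main Cox model in SAP 12.1 adjusts for baseline TTP. HIV status enters only in the sensitivity analyses and the adjusted column of Table 2.8. Neither site nor Ct is in any listed set for that model.

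**The case against.** The strongest reply is that this is loose drafting. The SAP never calls the rule deterministic; it speaks of a minimisation randomisation algorithm, and its introduction says it is to be read with the protocol, which supplies the random element. The last sentence of 4.2 may simply be an incomplete summary. That stands: the documents cannot show that allocation ran without a random element. The list may likewise be stray wording, since the same section says results are generated as patients are entered; nothing shows that a list was used.

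A reader might also infer that a site could work out its next arm. The figures do not support that: under the literal rule the own-site guess is wrong about 62% of the time, and most of its advantage over chance comes from minimising on site, which is the protocol's own choice. The 71% figure needs the running totals from all sites, whereas allocation is central, each site has its own account, and protocol 13.6 restricts cumulative summaries by arm to the DSMB.

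A further inference might be that the trial's tests are invalid. That goes too far. The primary efficacy analysis (SAP 10) is exposure-response modelling, which considers baseline bacterial load and HIV as covariates. Baseline TTP in the Cox model also carries part of the information in Ct.

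What remains is the textual conflict, the missing algorithm details, and the absence of site and Ct from the Cox model.

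**Conclusion.** The inconsistency is real. The protocol requires a chance element; SAP 4.2 states a rule without one and adds a list that does not fit it. If the SAP sentence is literally true, allocation departed from the protocol and was somewhat more predictable: about 38% correct own-site guesses, against 31% to 35.5% with a random element and 20% by chance. This rests on marginal-count minimisation and the assumed prevalences, site sizes and probabilities. If lowest allocation proportion means overall arm totals, own-site guessing is about 21% either way.

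Any effect falls on the secondary Cox comparisons and the arm-wise safety proportions; the primary exposure-response analysis is largely untouched. The point is worth correcting because it is specific and cheap, not because bias has been shown.

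**What to change.** 1. Check the configuration of the randomisation system and its allocation log.
2. Rewrite SAP 4.2 to state the algorithm actually used: assignment probability, imbalance measure, factor weights and tie-break. It should agree with the protocol or declare the departure. The probability must come from the system, because the protocol gives none.
3. Delete the reference to a predefined list, or explain what it is.
4. In the Cox arm comparisons, include HIV status and Ct as covariates, and site as a stratum or covariate if the data support it. With seven sites and 75 participants (about 75/7 = 10.7 per site), a fallback should be named in advance.
5. Only if the system ran without a random element: report the departure in the CSR and add a re-randomisation sensitivity analysis for the arm comparisons. With no chance element in the rule, the reference distribution has to be taken over ties and arrival order.

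The cost is a configuration check, a short SAP correction and a few extra model terms, plus one sensitivity analysis if step 5 applies. Enrolment was planned for Q3 2021 to Q1 2022, before the SAP's date, so this is probably a matter of describing and analysing what was done, not of changing allocation.

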4.3. Sample Size Determination

15 participants per arm with a total of 75 participants, and a wide range of DZD doses (from 0mg to 800mg BID) has been determined as an adequate sample size for population PK modelling, and for exposure response modelling to detect a clinically meaningful dose-dependent relationship.

Furthermore, the planned sample size of 15 participants per treatment group is in keeping with other trials of this type and accounts for the possibility of up to 3 drop-outs per group, which based on previous studies of this type conducted at these sites, represents a conservative estimate of the expected drop-out rate.

Previous Phase IIA (EBA) studies indicate that the between patient standard deviation of logCFU can be approximately 0.2. Therefore, assuming similar variability in this trial the expected standard errors of group mean EBA and corresponding width of 95% confidence intervals are 0.052 and 0.101 respectively for a group size of 15 and 0.063 and 0.124 respectively for a group size of 10.

This level of precision with a group size of 15 is considered adequate.

4.4. Early Stopping Rules

An independent data safety monitoring board (DSMB) will be convened for the trial. The DSMB will review safety data at regular intervals as defined in the DSMB Charter, but will also perform expedited review if the following conditions are met:

- Three or more participants experience a grade 3 or higher AE (CTCAE 5.0) in the same organ system that are at least possibly
 related to one of the study drugs, and qualify as "unexpected" by being more severe than in previous experience with the drug
 in question.
- Two or more participants experience a grade 4 or higher AE (CTCAE 5.0) in the same organ system that are at least possibly
 related to one of the study drugs, and qualify as "unexpected" by being more severe than in previous experience with the drug
 in question.
- One patient experiences a grade 5 AE (death) that is at least possibly related to one of the study drugs.

Refer to DECODE Protocol and DSMB charter for more individual patient safety stopping criteria.

5. Trial Endpoints

5.1. Primary Endpoint:

5.1.1. Primary Safety Endpoint

Participants will be regularly assessed for AEs during treatment and follow-up phase, including assessments of vital signs, physical examination, weight, detailed neurological examination, colour vision and visual acuity tests, 12-lead ECGs and routine clinical laboratory tests (including chemistry, haematology and urinalysis data).

The safety of DZD will be investigated by evaluation of:

Proportion of participants experiencing expected oxazolidinone class toxicities, defined as peripheral or optical
neuropathy, or incident leukopenia, anemia or thrombocytopenia, or adverse events in line with tyramine pressor
response, all of Grade 2 or higher, possibly, probably or definitely related to DZD.

5.1.2. Primary Efficacy Endpoint

The efficacy of DZD will be evaluated by measuring the change in mycobacterial load over time on treatment as quantified by time to positivity in BD MGIT 960® liquid culture described by nonlinear mixed-effects methodology (see section 10).

5.2. Secondary Endpoints:

See section 11 for fuller definitions of secondary endpoints.

5.2.1. Secondary Safety Endpoints

- All adverse events
- · Adverse events of Grade 3 severity or higher
- · Adverse events possibly, probably or definitely related to study drugs
- · Treatment discontinuations or interruptions related to adverse events/serious adverse events
- · Frequency, severity and type of ECG alterations
- Changes in ECG intervals of PR, RR, QRS, QT, Fridericia-corrected QT [QTcF]
- Proportion of participants with QTcF > 500ms in ECGs on treatment
- Proportion of participants with a prolongation of QTcF > 60ms in ECGs of grade 3 and above as defined in the protocol

5.2.2. Secondary Efficacy Endpoints

- Proportion of participants who suffer relapse, defined as recurrent disease caused by a strain indistinguishable to the baseline isolate (using whole genome sequencing), within 12 months post randomization, out of participants completing 16 weeks of therapy and achieving sustained sputum culture conversion defined as two successive negative liquid media cultures at or before WK08, with no positives to follow by the week 16 visit. Full definition of relapse in section 11.2.
- Time to recurrent TB, and to relapse, within 12 months post randomization.
- Time to culture conversion to negative on liquid media (defined as two negative cultures without an intervening positive culture).
- Proportion of participants converting to negative sputum culture in liquid media (defined as two negative cultures
 without an intervening positive culture) at each time point during treatment.
- Proportion of participants with negative sputum culture on solid media at WK 08 and other time-points.
- Proportion of participants developing drug resistance among those not converting to negative culture.

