5.4. Mycobacteriology Identification and Characterization Endpoint

Sputum cultures from various timepoints during the study will be assessed as follows:

- Minimum inhibitory concentrations (MIC) of BDQ, DLM, MXF, DZD of the infecting strain, at baseline and on representative isolate(s) grown at or after WK08, if any.
- · Frequency of acquired mutations in the infecting strain over treatment by whole genome sequencing
- Comparison between bacterial strain causing recurrent disease, and the strain at baseline by whole genome sequencing, to discriminate relapse from re-infection.

These assessments will be performed dependent on the availability of lab capacity and budget, so may not be completed for all possible timepoints.

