11.2. Relapse

An important secondary outcome is the proportion of participants who suffer relapse among those completing 16 weeks of therapy, achieve early culture conversion to negative in liquid media if there is a culture negative timepoint at two consecutive visits, the first of which is at or before week 08, without an intervening culture positive timepoint, and terminating therapy.

All participants will be classified as follows:

- Not achieved culture conversion to negative before or at week 8 after randomization (based on the analysis visit window).
 These participants will not end treatment at week 16 according to the protocol and therefore are not included in the relapse analysis.
- Relapse defined as having two consecutive culture positive timepoints without an intervening culture negative timepoint where the first occurs after Week 16 after randomization (based on the analysis visit window) and the recurrence strain of MTb is shown to be the same as that at baseline. If strain typing results are missing or inconclusive, a recurrence will be considered a relapse (rather than a reinfection).
- Reinfection defined as having two consecutive culture positive timepoints without an intervening culture negative timepoint where the first occurs after Week 16 after randomization (based on the analysis visit window) and the recurrence strain of MTb is shown to be different from that at baseline.
- Died at any point during the study
- Culture positive timepoint when last seen (not meeting criteria for other outcomes above)
- Culture negative timepoint when last seen (not meeting criteria for other outcomes above)

Outcomes will be tabulated by treatment arm among all in the ITT analysis population and among those in the AA analysis population.

A sensitivity analysis will be conducted repeating this relapse analysis using the second definition of time to culture conversion described below under the latter part of section 11.4.

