11.4. Time to culture conversion to negative on liquid media

Participants will be classified as having culture conversion to negative in liquid media if there are two consecutive culture negative timepoints without an intervening culture positive timepoint. Any other results will be ignored for the calculation of time to culture conversion. Culture timepoints will be classified as negative or positive according to the trial definition under 11.1.

Time will be taken from the date of randomization to the first occurrence of two consecutive negative culture timepoints.

Culture positive timepoints that occur after culture conversion has been achieved do not affect time to culture conversion.

This will be the primary definition of time to culture conversion. Primary analysis will be performed based on the primary definition. We will, in addition, perform two sensitivity analyses with alternative definitions of time to culture conversion:

- 1) The definition will be as above, with the exception that culture conversion can only be achieved if the two consecutive visits assessed as culture negative timepoints without an intervening culture positive timepoint are at least 28 days apart.
- 2) The definition will be as above, with the exception that culture conversion is only achieved provided no further culture positive timepoints occur after 'culture conversion', in the period up to and including the week 16 visits (a subsequent culture positive timepoint effectively 'cancels' out culture conversion).

12. Analysis Method

12.1. Analysis of time to culture conversion by dose group.

Descriptive summary statistics, such as mean/median of the time to culture conversion will be tabulated. Proportion of participants achieving culture conversion at each time point during treatment will be summarized using the Kaplan-Meier estimator with 95% confidence intervals.

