A Cox regression model will be used to compare each arm with different DZD doses to the background regimen without DZD, in time to culture conversion. The analysis will be adjusted for the baseline cultures using time to positivity (TTP) at the time of screening and enrolment. Demographic and clinical characters, such as gender, age, race, BMI, HIV status, smoking, alcohol usage, will also be adjusted in sensitivity analyses. To check the Proportional Hazard (PH) assumption, we will do statistical tests and graphical diagnostics based on the Schoenfeld residuals. ¹² If the PH assumption is violated, cox regression models will be presented but interpretation will take into account this violation and alternative methods will be added including restricted mean survival time ¹³.

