12.3. Development of drug resistance

Any changes in drug resistance profile from baseline will be listed including baseline and any follow-up drug resistance data, culture results, and treatment arm.

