% With culture conversion at 8 weeks	xx.x%	xx.x%	xx.x%	xx.x%	xx.x%
% With culture conversion at 12 weeks	xx.x%	xx.x%	xx.x%	xx.x%	xx.x%

% With culture conversion at 14 weeks	xx.x%	xx.x%	xx.x%	xx.x%	xx.x%
% With culture conversion at 16 weeks	xx.x%	xx.x%	xx.x%	xx.x%	xx.x%
Hazard Ratio (95% CI)	xx (xx, xx)				

 $Figure\ 2.1:\ Kaplan-Meier\ plot\ of\ time\ to\ first\ of\ two\ negative\ culture\ conversions.$

{including Kaplan - Meier plot comparing 4 arms with number at risk/control below}

Table 2.10 Summary of Relapse by Treatment Arm

Total in ITT analysis population	Arm 1 D0 (N=x) n (%)	Arm 2 D400 (N=x) n (%)	Arm 3 D800-OD (N=x) n (%)	Arm 4 D1200 (N=x) n (%)	Arm 5 D800-BD (N=x) n (%)	Total (N=x) n (%)
Not achieved time to stable culture conversion	xx (xx.x %)	xx (xx.x %)	xx (xx.x %)	xx (xx.x %)	xx (xx.x %)	xx (xx.x %)
Relapse	xx (xx.x %)	xx (xx.x %)	xx (xx.x %)	xx (xx.x %)	xx (xx.x %)	xx (xx.x %)
Time to relapse (mean +- SD)	xx (xx)	xx (xx)	xx (xx)	xx (xx)	xx (xx)	xx (xx)
Reinfection	xx (xx.x %)	xx (xx.x %)	xx (xx.x %)	xx (xx.x %)	xx (xx.x %)	xx (xx.x %)
Time to Reinfection (mean +- SD)	xx (xx)	xx (xx)	xx (xx)	xx (xx)	xx (xx)	xx (xx)
Death	xx (xx.x %)	xx (xx.x %)	xx (xx.x %)	xx (xx.x %)	xx (xx.x %)	xx (xx.x %)
Culture positive when last seen	xx (xx.x %)	xx (xx.x %)	xx (xx.x %)	xx (xx.x %)	xx (xx.x %)	xx (xx.x %)
Culture negative when last seen	xx (xx.x %)	xx (xx.x %)	xx (xx.x %)	xx (xx.x %)	xx (xx.x %)	(xx.x %)

Table 2.11 Summary of Drug resistance by Treatment and Visit:

Arm 1 D0 (N=x)	Arm 2 D400 (N=x)	Arm 3 D800-OD (N=x)	Arm 4 D1200 (N=x)	Arm 5 D800-BD (N=x)	Total (N=x)
----------------------	------------------------	---------------------------	-------------------------	---------------------------	----------------

Number of			
Participants			
Drug Name			
of			
Resistance			
Proportion			
of			
Participants			
developing			
drug			
resistance			
among those			
not			
converting			
to negative			
culture.			

Listing 2.1 Listing of all Drug Resistance

{This section will list a record of all drug resistance, including drug name, visit number, participant ID etc. F}

{Additional sensitivity analysis will be performed with alternative definitions of time to culture conversion, tables 2.8 and 2.9 will be repeated for each sensitivity definition of time to culture conversion.}

3. Safety Evaluation

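### The only defined summary proportion for acquired drug resistance uses non-converters as its denominator, so the by-arm figures are not a randomised comparison and omit resistance first found after conversion

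*SAP*

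**What the plan says.** Protocol 9.2.2 and SAP 5.2.2 give the same secondary efficacy endpoint: "Proportion of participants developing drug resistance among those not converting to negative culture". Shell Table 2.11 carries it as a row by arm, beneath two rows (a number of participants and the drug concerned) that it does not define.

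Other parts of the SAP are broader. Section 12.3 says: "Any changes in drug resistance profile from baseline will be listed including baseline and any follow-up drug resistance data, culture results, and treatment arm". Listing 2.1 is described as follows: "This section will list a record of all drug resistance, including drug name, visit number, participant ID etc". Neither is limited to non-converters. SAP 5.4 adds MICs on isolates grown at or after week 8, and "Frequency of acquired mutations in the infecting strain over treatment by whole genome sequencing". Those assessments depend on laboratory capacity and budget, and the acquired-mutation item has no stated denominator and no table shell.

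On conversion, SAP 11.4 requires two consecutive negative timepoints, sets no deadline, and adds: "Culture positive timepoints that occur after culture conversion has been achieved do not affect time to culture conversion". SAP 11.2 uses a week 8 cut-off for the relapse analysis and says of those who miss it: "These participants will not end treatment at week 16 according to the protocol and therefore are not included in the relapse analysis".

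Conversion is also an outcome compared between arms. SAP 12.1 states: "A Cox regression model will be used to compare each arm with different DZD doses to the background regimen without DZD". SAP 3.2.2 makes it an objective to assess increasing doses against the background regimen on the primary and secondary efficacy endpoints, of which resistance is one.

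**The concern.** A proportion among non-converters conditions on something that happens after randomisation and that delpazolid is meant to change. If a dose converts more participants, fewer remain in the denominator, and they are likely to be the harder cases. The proportion can then rise in the more effective arm even when the number of randomised participants who acquire resistance is the same.

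The numerator is cut in the same way. Under the primary definition in SAP 11.4 a later positive culture does not undo conversion. A participant who converts and then reverts or relapses with a newly resistant strain is therefore in neither numerator nor denominator. Yet the protocol stores isolates from every positive culture at or after week 8 (11.2) and from suspected recurrence (11.4), so some of the information may exist.

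At stake is a by-arm row that readers may take as a dose comparison, because the objectives invite one.

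**Working it through.** The documents give no resistance rate, conversion rate, alpha or power for this endpoint, so there is no figure of the plan's own to reproduce. The inputs are 15 participants per arm and up to 3 drop-outs per arm, hence 12 evaluable (SAP 4.3). Conversion rates c of 60% to 95% are assumptions.

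**1. Size of the denominator.** Expected non-converters = n(1 − c). The chance that an arm has none, which leaves the proportion undefined, is c^n.

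| Assumed c | Expected, n = 15 | Chance of none, n = 15 | Expected, n = 12 | Chance of none, n = 12 |
|---|---|---|---|---|
| 60% | 6.0 | 0.0% | 4.8 | 0.2% |
| 70% | 4.5 | 0.5% | 3.6 | 1.4% |
| 80% | 3.0 | 3.5% | 2.4 | 6.9% |
| 90% | 1.5 | 20.6% | 1.2 | 28.2% |
| 95% | 0.75 | 46.3% | 0.6 | 54.0% |

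For example, 0.90^15 = 0.206.

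**2. Same number of resistant participants, different conversion.** Suppose exactly one of 15 randomised participants acquires resistance and does not convert. Intervals are exact (Clopper-Pearson) 95%: for x of n, the lower limit is the 2.5% point of Beta(x, n − x + 1) and the upper limit the 97.5% point of Beta(x + 1, n − x).

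| Converters of 15 | Endpoint as defined | Over all 15 |
|---|---|---|
| 9 | 1/6 = 16.7% (0.4 to 64.1%) | 1/15 = 6.7% (0.2 to 31.9%) |
| 12 | 1/3 = 33.3% (0.8 to 90.6%) | 1/15 = 6.7% (0.2 to 31.9%) |
| 14 | 1/1 = 100% (2.5 to 100%) | 1/15 = 6.7% (0.2 to 31.9%) |

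Only the conversion of the other participants differs between rows.

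**3. A resistant case found at relapse.** Add one participant who converts and later relapses with a newly resistant strain. The endpoint as defined does not move. Over all 15 it becomes 2/15 = 13.3% (1.7 to 40.5%).

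**4. Which participants count as non-converters.** Suppose 9 of 15 convert by week 8 and 3 more later in treatment. Under the week 8 rule of SAP 11.2 there are 15 − 9 = 6 non-converters; under SAP 11.4, with no deadline, there are 15 − 12 = 3. One resistant participant who never converts is then 1/6 or 1/3 in the same arm. SAP 5.2.2, 12.3 and Table 2.11 do not say which applies. SAP 11.4 also has two alternative definitions of conversion, but the appendix repeats only Tables 2.8 and 2.9 under them.

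**The case against.** The strongest reply is that the resistance data are not restricted. SAP 12.3 lists every change from baseline with treatment arm, Listing 2.1 covers all resistance, and the acquired-mutation endpoint in SAP 5.4 has no converter restriction. The two undefined rows of Table 2.11 might also supply counts by arm that a reader could divide by the arm total. This stands. A reader might infer that resistance is reported only among non-converters, and the documents do not support that. What is missing is a defined rate on the randomised denominator; a listing gives none, and neither undefined row is specified as one.

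A second reply is that resistance can be measured only where organisms still grow, so restricting to non-converters is a reasonable description. This stands in part. Over all ITT participants, anyone without a late isolate counts as having none detected, so that figure partly restates conversion. Detection is also uneven: participants referred for further treatment do not have the week 26 and 38 visits (Protocol section 2, footnote A). Neither denominator is clean, which is why both should be shown.

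Third, no between-arm test or decision rule uses this proportion, and the intervals above overlap widely. A reader might infer that the plan would lead to a wrong dose being chosen. The documents do not support that; the risk is a misread table. A reader might also suppose that preventing resistance is why delpazolid is added. The rationale in Protocol section 5 speaks of dose selection, exposure-response and a regimen with low pre-existing resistance, which is a different matter.

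Finally, testing of recurrence isolates is not assured, because SAP 5.4 makes it depend on capacity and budget.

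**Conclusion.** The point holds as a limited weakness in one secondary endpoint. The only explicitly defined summary proportion conditions on a post-randomisation outcome, so its arm values are not a randomised comparison, and it leaves out resistance first detected after conversion or at relapse. It may rest on very few participants: about three per arm at 80% conversion, and at 90% a one-in-five chance of none. The same single case can read as 16.7%, 33.3% or 100% where the randomised proportion is 6.7% throughout.

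The sizes rest on assumed conversion rates and illustrative case counts. That the denominator is post-randomisation, and that later resistance falls outside it, follows from the definitions alone. The undefined timepoint for non-conversion is a separate gap that needs no assumption. This is a cheap improvement to reporting and does not threaten the primary analysis.

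**What to change.** - Add a row to Table 2.11, with a matching sentence in SAP 12.3: number and proportion of all ITT participants per arm with detected acquired resistance to any study drug up to week 52, including any recurrence isolates tested, with exact 95% intervals.
- Footnote that participants without a late isolate count as none detected, that the figure therefore partly reflects conversion, and that testing depends on laboratory capacity and budget.
- Keep the non-converter proportion as a descriptive row, with its denominator shown for each arm.
- State which definition and timepoint make a participant a non-converter: the week 8 rule of SAP 11.2, or SAP 11.4 with an explicit deadline.
- Reconcile which MICs are measured. Protocol section 10.5.2 refers to the drugs a participant is receiving, whereas the susceptibility-testing footnote to the schedule of events refers to the study drugs. This decides whether delpazolid resistance can be counted in the arm without delpazolid.

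The cost is one table row, a footnote and a definition. No new data are collected and the protocol endpoint stays as it is. The row is complete only at the final analysis, once week 52 data are in. Its downside is the undercount among participants without a late isolate, which the footnote discloses but does not remove.
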